5.4 Storage

Storage in the Investigational Pharmacy should be at room temperature.

5.5 Study Agent Administration

The Institutional Investigational Pharmacy will be responsible for receiving, inventory and dispensing of study agent after documentation of local IRB approval of the KUMC-approved protocol and consent.

Study agent will be dispensed with the study number of each subject. All subjects will be given 200 capsules (two bottles) of study agent at the baseline visit. This provides sufficient study agent to accommodate a 2-3 week delay in scheduling of procedures or travel. If additional study agent is required because of extended delays in scheduling, it may be shipped to the subject. At the 6-month visit, the unused study agent will be counted for compliance, but then returned to the subject. An additional 200 capsules (two bottles) will be dispensed for the remainder of the study. Again, if additional study agent is required because of extended delays in scheduling, it may be shipped to the subject.

The study coordinator will give the study agent to the subject with instructions to take one capsule at approximately the same time of day in conjunction with intake of food and at least eight ounces of water and to keep track of missed doses or lost capsules.

5.6 Blinding and Unblinding Methods

In the event of a serious adverse event or other circumstance requiring unblinding, in the opinion of the responsible physician, the site investigator will notify KUMC. The KUMC statistician will unblind the subject to the site investigator if necessary. If the treatment blind is broken, the reason and the date should be recorded and signed by the investigator.

5.7 Agent Destruction/Disposal

At the completion of investigation, all unused study agent will be destroyed in accordance with each site's investigational pharmacy regulations

5.8 Concomitant Medications

Subjects are not allowed to start flaxseed, or lignan supplements, tamoxifen, raloxifene, anastrozole, letrozole or any other SERM or aromatase inhibitor or investigational drug while participating on this trial. Subjects may not alter their use of oral or non-oral hormonal contraceptives.

Subjects are strongly encouraged to continue any routine medications throughout the duration of the study to avoid confounding adverse events due to starting and stopping other medications while on study.

All medications (prescription and over-the-counter), vitamin and mineral supplements, and/or herbs taken by the participant will be documented on the concomitant medication CRF and will include: 1) start and stop date, dose and route of administration, and indication. Medications taken for a procedure (e.g., biopsy) should also be included.

5.9 Dose Modification

Dose modifications will not be utilized for this study. Because study agent is only available in a single dose capsule, no dose modification option is available. If a subject is experiencing adverse events or is having a medical procedure that requires a brief suspension of SDG, this must be noted in the CRF on the dose suspension page. At the discretion of the PI, subjects may be removed from participation for significant dose suspension time periods.

Subjects with grade 2 adverse events considered to be related to study agent will have the agent suspended until the toxicity has resolved. The agent will then be resumed. If toxicity again occurs, and is thought to be agent-related, the agent will be permanently stopped. Grade 2 hot flashes or menstrual irregularities will not be cause for suspending study agent.

Subjects who experience grade 3-4 toxicity will have the study agent suspended. The agent may be re-instituted after resolution of the adverse event, providing the investigator feels relatively certain that the toxicity is not due to the study agent and that resuming agent will not affect recovery from the condition

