5.0 AGENT ADMINISTRATION

5.1 Dose Regimen and Dose Groups

Both Brevail® and matched placebo are to be provided by Lignan Research, Inc. to the investigational pharmacy at each participating institution.

Brevail® (containing 50 mg of the active ingredient SDG) or placebo (containing the same filler material but without SDG) will be given to all trial participants for the 12 months of participation. All subjects should have off-study procedures no later than within 36 hours of the last dose of SDG or placebo. However, if a participant stops study agent prematurely in an unscheduled situation, she should come in for biomarker re-assessment as early as possible.

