5.10 Interruption or Discontinuation of Treatment

A genuine effort must be made to determine the reason(s) why a subject fails to return for the necessary visits or is discontinued from the trial. Information regarding the reason for not completing the trial will be recorded on the appropriate case report forms.

It will be documented whether or not each subject completed the clinical study. If for any subject study treatment or observations were discontinued the reason will be recorded on the appropriate case report form. Reasons that a subject may discontinue participation in a clinical study are considered to constitute one of the following:

- adverse event(s)
- abnormal laboratory value(s)
- abnormal test procedure result(s)
- subject develops breast cancer
- protocol violation
- subject withdrew consent
- lost to follow-up
- administrative problems
- physician decision
- death

All subjects that discontinue trial prematurely require notification of the Protocol Chair or her designee at KUMC within 72 hours of known discontinuation.

Any subject who receives at least one dose of study agent will be included in the safety analysis.

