11.2 Statistical Analysis

All analyses will be intent-to-treat. All subjects randomized will be evaluable for safety and all subjects that have both a pre and post specimen are evaluable for efficacy. Primary analysis of efficacy will be performed on all evaluable subjects and secondary analysis will be done on those subjects who received at least 6 months of study medication and were confirmed as being in the follicular phase for both RPFNA procedures. From our experience we have very little missing data; however, if the missing data rate is above 5%, we will use multiple imputation to impute these values to perform the primary and secondary analyses.

The primary outcome will be change in Ki-67 (percent of cells expressing Ki-67) from baseline to 12 months. The two-sample t-test will be used to compare the change in Ki-67 between the SDG

and placebo groups. Any difference in baseline values of Ki-67 between the two groups would be due to chance, however, if there is a significant difference, then analysis of covariance adjusting for baseline values will be performed. Due to potential skewness in these variables we will assess whether or not the Central Limit Theorem may be assumed. Given the sample size the existence of an extremely high degree of skewness would require the use of the Wilcoxon Signed Rank test.

For the secondary endpoints, similar methods as above will be used to compare the treatment and control groups at two time points for all markers, i.e., serum hormones and clinical laboratory tests. We will also correlate change in the primary biomarker Ki-67 with change in other markers (e.g., bioavailable estradiol, cytokines, RTqPCR results) using Pearson's correlation coefficient. Again, if there exists a high degree of skewness in these variables, Spearman's correlation will be utilized.

Multiple regression analysis will also be used to investigate whether changes in Ki-67 are due to variables other than treatment effect (e.g., age, cytromorphology, Gail risk; as well as the predictive effect of other biomarkers on modulation of Ki-67). Best subsets and stepwise approaches will be employed while controlling for treatment group.

For comparison of moderate or worse toxicities we will consider grade 3 toxicity or premature trial discontinuation as the critical events. The prevalence of events in the SDG vs. the placebo arm will be examined by Fisher's exact test.

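### Section 5.9 lets a dose suspension end a woman's participation, not only her dosing, so low exposure can take her out of the intent-to-treat primary analysis; the likely bias is very small

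*Combined protocol and SAP*

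**What the plan says.** Section 5.9 handles toxicity by acting on the agent, which is suspended, resumed or stopped for good; for recurrent grade 2 events, "If toxicity again occurs, and is thought to be agent-related, the agent will be permanently stopped". One sentence goes further: "At the discretion of the PI, subjects may be removed from participation for significant dose suspension time periods". No duration or other criterion defines what counts as significant.

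Section 5.10 treats stopping agent and ending observation as different things, since it says "If for any subject study treatment or observations were discontinued the reason will be recorded on the appropriate case report form". Its list of reasons for discontinuing participation includes a physician's decision.

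Section 11.2 opens with "All analyses will be intent-to-treat". It then defines efficacy evaluability: "all subjects that have both a pre and post specimen are evaluable for efficacy". The primary analysis uses those evaluable women. Exposure appears only in the second tier: "secondary analysis will be done on those subjects who received at least 6 months of study medication", together with confirmed follicular phase at both aspirations.

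Two provisions soften this. Section 5.1 says "if a participant stops study agent prematurely in an unscheduled situation, she should come in for biomarker re-assessment as early as possible". Section 11.2 says "if the missing data rate is above 5%, we will use multiple imputation to impute these values", without naming the variables in the imputation model or the denominator of the missing-data rate.

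**The concern.** Whether a woman accumulates a long dose suspension is decided after randomisation, and suspensions follow adverse events or medical procedures. If the investigator then ends her participation and no post RPFNA is taken, a protocol rule has excluded her from the primary analysis for low exposure. Section 11.2 meant exposure to restrict only the secondary analysis.

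If the removed SDG women have less Ki-67 reduction than those who stay, the estimate moves away from the as-randomised effect towards the effect in women who stayed on agent. Her 12-month questionnaires, which serve the quality-of-life objective, can be lost in the same way. Other causes of a missing specimen also pass through the 11.2 definition; this point concerns only the loss that a stated rule permits.

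**Working it through.** **Inputs.** From 11.1 and 11.2: 220 evaluable women, 2:1 allocation (147 SDG, 73 placebo), difference 2.5 points, SD 6, two-sided 5% t-test. From 4.5.1: 242 randomised. From 2.4.4.1: median pilot compliance 96%. The documents give no rate of removal by the investigator, so p = 2%, 3% and 5% of SDG women are assumptions.

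**1. The plan's power.** SE = 6 × √(1/147 + 1/73) = 0.859. Then 2.5/0.859 = 2.91, and normal power is Φ(2.91 − 1.96) = 0.829. With the t distribution it is 82.6%. The stated 83% is reproduced.

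**2. Women involved.** 242 × 2/3 = 161 SDG women; 2%, 3% and 5% of these are 3, 5 and 8.

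**3. No post specimens, no imputation.** With no remaining effect in removed women, the as-randomised effect is 2.5 × (1 − p), while the analysis estimates 2.5.

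| p | As-randomised effect | Overstatement | In SE units | Overstatement if half the effect remains |
|---|---|---|---|---|
| 2% | 2.450 | 0.050 | 0.06 | 0.025 |
| 3% | 2.425 | 0.075 | 0.09 | 0.038 |
| 5% | 2.375 | 0.125 | 0.15 | 0.063 |

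The overstatement is p times the effect lost. If SDG has no effect and removal is equal in both arms, it is zero.

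**4. Half of the removed women re-assessed under 5.1.** The analysed effect is 2.5 × (1 − p)/(1 − p/2) = 2.475, 2.462 and 2.436. The overstatement is 0.025, 0.037 and 0.061.

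**5. Imputation.** The 5% trigger is 0.05 × 242 = 12.1, so up to 12 women can be missing without imputation. The planned loss of 22/242 = 9.1% exceeds the trigger if the rate is counted over randomised women. If it is counted over evaluable women, absent post specimens never trigger it, because evaluable women have both specimens by definition. Suppose the model uses arm and baseline Ki-67 only, which is an assumption. A removed SDG woman is then given values like those of SDG women who stayed, so the bias in step 3 should remain. A simulation agrees (12,000 trials, 161 against 81 women, 9.1% total loss, equal removal in both arms, 10 imputations). The overstatement is 0.049, 0.071 and 0.125 (Monte Carlo SE 0.002), or 0.021, 0.032 and 0.058 with half re-assessed.

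**6. Power if removed women are kept.** Adding 3, 5 or 8 SDG women with no remaining effect:
- 150 against 73, effect 2.450: 81.3%
- 152 against 73, effect 2.425: 80.7%
- 155 against 73, effect 2.375: 79.3%

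With half the effect remaining, power is 82.1%, 81.9% and 81.3%. The largest loss is 82.6 − 79.3 = 3.3 points. If 5% of the 81 placebo women (4) are also returned, giving 155 against 77, power is about 81%, so the cost is smaller.

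**The case against.** The strongest reply is that the protocol already covers this woman. Section 5.1 does not limit who initiated the stop, and a woman removed after a long suspension has stopped agent early and off schedule. Nothing in 5.9 forbids her off-study RPFNA, and if she has one she is in the primary set. Section 5.1 also uses the word participation for the dosing period, so an agent-only reading of 5.9 is possible. This stands in large part and is why the likely bias is very small. It does not settle the matter: 5.1 says only that she should come in, 5.9 does not point to it, it leaves out questionnaires, and the contrast within 5.9 between stopping agent and ending participation favours the wider reading.

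A second reply is that the exclusion comes from the pre-and-post rule in 11.2, which applies to every missing specimen, and that 5.10 would still let an investigator end participation as a physician's decision. Both are correct. The second means that an edit to 5.9 alone would leave the same exit open.

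A reader might infer that this route could produce a false positive, or that removals would favour one arm. The documents support neither. The modelled bias vanishes if SDG has no effect and removal is equal, site and coordinating staff and participants are blinded (4.6.2), and nothing shows how removals would fall by arm.

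A reader might also infer that the edit plus imputation brings the bias to almost nothing. In simulation, with half of the removed women re-assessed, the overstatement falls below 0.01, but only when exposure and its interaction with arm are added to the imputation model. Exposure data will exist, since 5.11 collects pill counts by half-year, but neither the plan nor this edit specifies such a model, so that result is not evidence for the edit.

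**Conclusion.** The point holds as a cheap, low-priority improvement. Sections 5.9 and 11.2 together permit an exposure-based exit from an analysis described as intent-to-treat, and 5.1 narrows that exit without closing it.

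The largest overstatement considered, 0.13 points or 0.15 SE, needs 5% removal, no post specimens and no remaining effect all at once. High pilot compliance makes that combination unlikely. With half re-assessed it is about 0.02 to 0.06 points. All these sizes rest on assumed removal rates. The stated power is not in error, and nothing here suggests that the trial's conclusion would change.

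**What to change.** In 5.9, replace removal from participation with *discontinued from study agent*. Add: *Unless she withdraws consent or RPFNA is clinically contraindicated, she has the off-study RPFNA, blood draw and questionnaires under the early re-assessment rule in 5.1, and is analysed in her randomised arm.* If RPFNA is contraindicated, the blood draw and questionnaires still go ahead.

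In 5.10, record stopping agent separately from ending observations. State that a dose suspension or low exposure alone, including when entered as a physician's decision, ends agent only. The undefined threshold in 5.9 then no longer affects who is analysed. The rules for suspending or stopping agent and the timing in 5.1 stay as they are.

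The cost is a few sentences and no new procedure, since 6.1 and 6.5 already plan these assessments for every randomised woman. The estimate is slightly diluted, and power falls by about 1 to 3 points if removed women keep no effect.

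The edit has two limits. An early specimen is not a 12-month value. The edit also leaves the imputation model and the denominator of the 5% rule unspecified, so no near-zero residual bias should be claimed for it.

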5.10 Interruption or Discontinuation of Treatment

A genuine effort must be made to determine the reason(s) why a subject fails to return for the necessary visits or is discontinued from the trial. Information regarding the reason for not completing the trial will be recorded on the appropriate case report forms.

It will be documented whether or not each subject completed the clinical study. If for any subject study treatment or observations were discontinued the reason will be recorded on the appropriate case report form. Reasons that a subject may discontinue participation in a clinical study are considered to constitute one of the following:

- adverse event(s)
- abnormal laboratory value(s)
- abnormal test procedure result(s)
- subject develops breast cancer
- protocol violation
- subject withdrew consent
- lost to follow-up
- administrative problems
- physician decision
- death

All subjects that discontinue trial prematurely require notification of the Protocol Chair or her designee at KUMC within 72 hours of known discontinuation.

Any subject who receives at least one dose of study agent will be included in the safety analysis.

5.11 Adherence/Compliance

At the end of treatment the actual quantity of unused study agent will be compared to the anticipated amount of unused study agent. At the six month visit, after being counted by the study coordinator, the unused agent will be returned to the subject.

Subjects that maintain 70% of study agent intake as measured through patient reports and tablet counts conducted by the trial coordinator will be considered "compliant". Percent intake will be computed as the number of tablets taken divided by the number of days subject should have taken capsules. Pill counts and compliance will be considered separately for the first six and the last six months in the analysis.

6.0 CLINICAL EVALUATIONS AND PROCEDURES

6.1 Schedule of Events

Evaluations Procedures	Eligibility/ Pre-study visit	On Study Visit	Phone Contacts Months 1,3,9	6 Month Visit	11 Month Visit	12 Month Visit	2 Week Follow up Phone Contact
Informed Consent	X	X					
Height/Weight, Vital Signs	X	X				X	
Breast Exam	X ^c	X ^c				X	
Serum hormone assay only if non-menstruating	X ^d				X ^d		
RPFNA (day 1-10 of menstrual cycle)	X ^a					X ^a	
Serum/Plasma collection for hormone + lignan assays	X ^b					X ^b	
Screening eligibility checklist	X						
CBC + Fasting blood for chem. Profile, lignan and cytokine c-peptide		X ^{bc}				X ^b	
Urine collection (spot required, additional overnight preferred, materials to subject for menstrual diary)		X ^b				X ^b	
Medical History		X ^c					
Physical Exam		X ^c				X	
Urine Pregnancy Test		X					
Buccal sample		X ^b					
BCPT Symptom Checklist, BPQ Breast pain and lignan intake questionnaires		X				X	
Concomitant Meds.		X	X	X		X	X
Dispense Study Agent		X		X			
Adverse Events			X	X		X	X
Return Study Agent/Evaluate Compliance				X		X	
Off Study Evaluation							X

^a See specimen management section 7.0 for details on shipping of RPFNA materials to KUMC

^b To be shipped to KUMC for central analysis. See specimen management section 7.0. Notify KUMC by fax and email prior to shipment.

^c Physical, Breast exam, Baseline CBC, Medical history and fasting chem profile may be performed at RPFNA or Study Entry Visit as long as within 3 months prior to study entry.

^d If non-menstruating, blood assayed for hormone levels 2-4 weeks prior to anticipated RPFNA so as to predict timing of follicular phase.

6.2 Pre-Study Procedures and Evaluations

6.2.1 Mammography and Clinical Breast Exam.

Pre-study mammography is not a requirement for this study unless the potential subject is of sufficient risk for development of breast cancer that they are undergoing annual screening. In that case potential subjects must have had a normal mammogram within 9 months of baseline RPFNA. Subjects must have a clinical breast exam at baseline that is judged as being non-suspicious for breast cancer.

6.2.2 Pre-RPFNA instructions

Use of systemic antibiotics must be stopped for 3 weeks prior to RPFNA. Subjects will be told to discontinue aspirin products, fish oil, vitamin E, and NSAIDs at least 3 weeks prior to the RPFNA to reduce risk of excessive bleeding. Subjects should also be told to take 10 mg of vitamin K for 3 days prior to the RPFNA and to eat a good breakfast the day of the procedure. Vitamin K is strongly advised to reduce bleeding, but failure to take Vitamin K will not render a subject ineligible. Likewise, failure to discontinue fish oil or Vitamin E, or ingestion of an occasional aspirin or NSAIDS, will not render a subject ineligible. If subjects take an anti-anxiety medication such as ativan the day of the procedure they must have someone drive them home from the procedure. Otherwise they should be able to drive themselves.

For non-menstruating women (see section 4.2.4), hormone levels (estradiol, progesterone, and FSH) must be assayed 2-4 weeks prior to RPFNA in order to predict when to perform RPFNA so as to be in the follicular phase. Lab results and institutional normal ranges must be reviewed by the Protocol Chair, who will provide an acceptable time window within which to conduct the RPFNA.

6.2.3 Pre-study Eligibility Visit - RPFNA Procedure

Breast tissue acquisition will be performed between day 1 and 10 of the menstrual cycle. RPFNA will be performed under local anesthesia from both breasts (two sites on each breast or one unaffected breast in the case of prior DCIS or invasive cancer). The breast skin will first be cleansed with betadine and alcohol swabs. Two weals per breast with local anesthesia (typically 1% lidocaine with added epinephrine 1:100,000 buffered with bicarbonate) are made using a tuberculin (1 cc) syringe in the skin at ~ 2 and 10 o'clock within 4 cm of the areola, avoiding obvious blood vessels. After skin weals are placed, 4-5 cc of the same mixture is injected deeper into the breast tissue at the 2 sites. For women who have a hypersensitivity to epinephrine, lidocaine without added epinephrine should be used.

Six needle passes per site for the outer quadrants and four for the inner quadrants are performed with pre-wetted 10-12 cc syringes (sterile RPMI or PBS) with 21 gauge 1½ inch needle, within the anesthetic weal sites to withdraw epithelial cells lining the ductal tree. The clinician will preferentially sample areas in which resistance (density) is appreciated with the tip of the needle.

At KUMC and institutions with liquid nitrogen available in the clinic, the first two passes from each site in the breast will be expelled into labeled cryovials containing PBS (provided by KUMC) and immediately flash frozen by placing in liquid nitrogen. It is critical that bloody material not be placed into these cryovials as it ruins the assays.

Material from the remaining 14 passes (20 passes for institutions not participating in the flash frozen RPFNA substudy) in both breasts will be expelled and pooled into a single labeled 15 cc tube containing modified Cytolyt™ (9 cc Cytolyt™ and 1 cc 10% neutral buffered formalin). Fluid from the Cytolyt™ tube should be drawn into the needle/syringe hub approximately four times when expelling material into tube solution. Cell material should not be expressed against the side of the tube. Tubes are then placed on a tube rocker for approximately 12-24 hours prior to shipment to KUMC.

After the procedure, subjects will have ice packs placed on the breast for 10-15 minutes to control swelling and bleeding. Subjects are then wrapped with gauze cling wrap to create pressure on the puncture sites. A snug bra is also strongly recommended. Subjects are advised to limit strenuous physical activity over the next 24 hours and to report any pain or signs of infection.

Subjects may be offered analgesics after the procedure in order to control any pain that may occur.

